9.2 Time Period and Frequency for Event Assessment and Follow-Up

Unanticipated problems will be recorded in the data collection system throughout the study.

The PI and staff personnel will record all reportable events with start dates occurring any time after informed consent is obtained until 30 days after the last day of study participation. At each study visit, the study staff will inquire about the occurrence of AE/SAEs since the last visit. Events will be followed for outcome information until resolution, returns to baseline or stabilizes. If the AE does not meet these outcomes within 30 days after discontinuation of Erenumab or the end of the study, the participant will be referred to an appropriate practitioner for continued care.

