gets pregnant, decides to breastfeed her baby or father a child while taking erenumab will be withdrawn from the study and will be monitored and referred to an appropriate practitioner for continued care (see section 9.2 and 9.4.1).

Participants will be closely monitored for any AEs, during the clinic visit and between visits by telephone. Potential risks and discomforts will be clearly stated in the ICF.

Quantitative Sensory Testing (QST): A QST examination will assess sensory impairment by applying different stimuli in different body parts, and extraorally such as pressure or heat to the skin.

Extraoral sensory testing: The quantitative sensory testing (QST) will include stroking and/or applying gentle pressure with a brush, in the face. The examination will also include applying pressure with a probe on fingers, head and shoulders, and applying a heat sensor on the forearm. The test will be performed extraorally ipsilateral and contralateral to the area of pain. The potential, risks is a slight risk of tissue trauma or burning but this is avoided because the procedure is under the control of the examiner and the subject can stop it at any time. Study personnel will be trained and calibrated to perform these procedures.

General sensory testing:

Thermal (heat) stimulation: The potential risk involves burning of the skin (ventral forearm) This will be avoided with the thermal probe temperature not exceeding 50 degrees Celsius. The research staff will take the following precautions against potential burn risk: 1 1) provisions for immediate stimulus removal by the subject, and 2) provisions for skin temperature and duration of thermal stimulus by the researcher to include a built-in minimum and maximum temperature limitation system in the thermal stimulator. Discomfort of the subject will be minimized by delivering stimuli that are below the subject's self-reported thermal pain tolerance level.

Mechanical cutaneous sensitivity: The potential risk involves transient discomfort. This is performed with weighted probes (2mm diameter; 8–512 mN forces) applied to the dorsum of digits 2, 3, and 4 of the left hand. Participants will be instructed to signal (verbally or by raising the right hand) when the sensation first becomes painful at which time the researcher will remove the probe. Because the probe is completely under the control of the examiner, there is little opportunity for bruising from this procedure.

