6.5 Assessment of Subject Compliance with Study Product Administration

Participants will receive the medication or placebo injection by a trained study staff member once a month on Visits 1, 2 and 3.

Between visits, study personnel will contact participants by telephone to assess study drug tolerance (AEs), and to remind them when they are scheduled for another dosage.

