7.4 Follow up and final Study Visit, Visit 5 (Day 112 +/- 3 days, 4 weeks after Visit 4)

- Review Daily Symptom Diaries in eCRF or collect and review it in paper forms
- Assess compliance with Daily Symptom Diaries
- Review 4 questionnaires from Visit 4 in eCRF or collect and review the paper forms
- Review medical history
- Record concomitant medications and therapies
- Take blood pressure and collect weight
- Assess and record adverse events (AEs)
- Perform urine pregnancy test (in women of childbearing potential)
- Provide final instructions to subject (in case of AE showing later)
- Complete a disposition form

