7.5 Withdrawal Visit

An early termination visit will be performed if a participant is suspended before the completion of the study, prior to withdrawal of consent and with the participant's permission. This could happen during a scheduled or unscheduled visit. The investigator, study coordinator or research staff will discuss with the participant to contact the research team in case AE arise after the withdrawal visit. The assessment and procedures of Visit 4 will be conducted at this visit.

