9 ASSESSMENT OF SAFETY

9.1 Specification of Safety Parameters

This study involves the use of Erenumab, a fully human monoclonal antibody that is a CGRP antagonist FDA approved for the management of chronic migraine.

The participants of this study will be closely monitored and follow up in their clinic visits and between visits with telephone calls. As part of the study outcomes, the study staff will record information regarding AEs. Overall health parameters will be captured on case report forms. These will be completed at every visit and data will be compiled for review by the IRB and AMGEN.

The description of potential risks is described in 2.3 and 6.3. The most common side effects of the use of Erenumab are:

Injection site reactions: which may include tenderness, pain, redness, itching,

bruising, firmness, or hypersensitivity

- Constipation
- Muscle spasms/Cramps
- Itching (pruritus)

Allergic reactions can happen within hours to days after using erenumab. Therefore, after the injection is administered, the participant will wait in the room for 20 minutes and the evening of the treatment visit, the participant will receive a follow up phone call and the information will be recorded.

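### Adverse events are to be recorded for 30 days after last participation, but no scheduled enquiry about new events falls after Visit 5 or the early-termination visit

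*Combined protocol and SAP*

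**What the plan says.** Section 9.2 sets the recording window: reportable events with a start date "any time after informed consent is obtained until 30 days after the last day of study participation". The method it gives is "At each study visit, the study staff will inquire about the occurrence of AE/SAEs since the last visit".

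Other sections add telephone contact while the participant is on study. Section 2.3.1 promises monitoring "during the clinic visit and between visits by telephone", section 6.5 repeats this for drug tolerance, and section 9.1 adds that on "the evening of the treatment visit, the participant will receive a follow up phone call".

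At the end of participation the arrangement changes. The Visit 5 checklist in section 7.4 has the item "Provide final instructions to subject (in case of AE showing later" and no later contact. At the early-termination visit (section 7.5) staff "will discuss with the participant to contact the research team in case AE arise after the withdrawal visit". In Appendix A the adverse event review row ends at Visit 5 and early termination, and the row for scheduling the next visit ends at Visit 4.

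There are two exceptions. Under 5.5.2 and 9.2, an event present at discontinuation is followed until it resolves, returns to baseline or stabilizes, with referral if it is unsettled at 30 days. Under 9.4.5, a pregnancy that occurs on study drug is followed to its outcome. Section 5.5.1 points the other way: if consent is withdrawn and the early-termination visit refused, staff make no attempt to obtain more data.

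**The concern.** The plan defines a window for new events but schedules no enquiry inside its last 30 days. In that stretch, capture of a new event depends on the participant choosing to call, whereas up to the last visit staff ask. Counts from the two periods are not ascertained in the same way.

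The length of active enquiry after the last dose also depends on how a participant leaves. A completer is questioned for eight weeks after the third injection. Someone who leaves shortly after an injection may be questioned for only a few days. If leaving differs between arms, so does the length of active safety follow-up. With about 20 participants per arm and descriptive safety summaries, one or two missed events could change the picture.

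**Working it through.** No figure in the plan is in dispute. The check places every described enquiry on the schedule and compares it with the window.

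**Where participation ends.** Baseline lasts 4 weeks (section 7.2). Randomization follows within 7 days (5.4.1) and Visit 1 within a week of that (7.2.1), adding 0 to 2 weeks. Visit 1 to Visit 5 is 112 days, or 16 weeks (7.4). The total is 4 + (0 to 2) + 16 = 20 to 22 weeks. This contains the stated 21 weeks, so for a completer participation ends at Visit 5. For an early leaver I take it to end at the early-termination visit; the plan does not define this.

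**Completers.**
- Last dose: Visit 3, Day 56. Last enquiry: Visit 5, Day 112.
- Active enquiry after the last dose: 112 − 56 = 56 days, matching the 8 weeks in section 4.
- End of window: 112 + 30 = Day 142, which is 142 − 56 = 86 days after the last dose.
- No enquiry scheduled: days 57 to 86 after the last dose.

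The second part of Appendix A heads the same visits Day 60 and Day 120. On that reading active enquiry is 120 − 60 = 60 days and the unqueried stretch is days 61 to 90. The conclusion is the same.

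**Early leavers.** Let d be the days from the last injection to the early-termination visit. Active enquiry lasts d days, and the unqueried stretch is days d + 1 to d + 30 after the dose. The plan gives no distribution for d, so these values are illustrative:

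| d | Active enquiry after last dose | No scheduled enquiry |
|---|---|---|
| 3 | 3 days | days 4 to 33 |
| 14 | 14 days | days 15 to 44 |
| 28 (e.g. leaving at Visit 4) | 28 days | days 29 to 58 |

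The smaller d is, the more of the first month after a dose goes unqueried.

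**How many.** Section 12.2 assumes 15% dropout: 0.15 × 40 = 6. This is an upper bound on early leavers with a short d. It includes people who leave late, people already followed for an ongoing event, and people who refuse further contact.

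**The case against.** The strongest reply is that passive reporting after the last visit is a stated choice. Section 9.2 says that events starting in the window will be recorded; it does not promise a further call. Participants are told at Visit 5 and at early termination what to do if something arises, and section 7.6 allows unscheduled visits for an adverse effect. This stands to the extent that the plan is not contradictory here. But discretionary visits and participant calls are not systematic capture.

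Four stronger readings are tempting, and the documents do not support them.

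- **That there is no contact at all after the last visit.** Ongoing events and pregnancies are followed, and a new event could surface during that follow-up.
- **That follow-up is shortest in those who react to the drug, because reactions are a main reason for leaving.** The plan gives no breakdown of the 15%. It lists other routes out: inadequate rescue (6.6.4), starting certain non-drug therapies (6.6.5) and voluntary exit (5.5.1). Participants withdrawn for hypersensitivity, constipation or hypertension (6.3) leave with an event that must be followed. For them the gap is a second, separate event.
- **That the window will appear free of events.** Participants may call, so the supportable statement is under-ascertainment of unknown size.
- **That the safeguards in 9.1 do not match the delayed onset of allergic reactions described there.** The evening call, the between-visit calls and the symptom inventory at visits together cover later onset while the participant remains on study. Whether those calls are repeated in section 7 or Appendix A is editorial.

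The footnotes to Appendix A were not in the text available for this review, so a call described only there cannot be excluded. Sections 7 and 9 mention none after Visit 5 or early termination.

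**Conclusion.** The point holds for new-onset events. Followed as written, the plan ascertains the last 30 days of its own window only passively. For completers little is lost, since the stretch begins eight weeks after the last dose. For those who leave soon after an injection it can cover most of the first month after that dose. The number concerned is at most about 6 of 40, and the true number depends on withdrawal timing, which the plan does not give.

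This rests on participation ending at Visit 5 or the early-termination visit, and on no later call being specified in the Appendix A footnotes. It is a worthwhile, inexpensive improvement to safety data collection, not an error that threatens the trial. The primary and secondary efficacy analyses do not depend on it.

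**What to change.** Add to sections 7.4 and 7.5, and as a column or row in Appendix A, one telephone enquiry about new adverse and serious adverse events 30 days after last participation. It would apply to everyone who has not withdrawn consent to contact. If resources are limited, give priority to those who leave early. Record whether the participant was reached, so that an unanswered call is not read as no event.

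Reconcile section 9.2 with section 5.5.1: state whether the 30-day window applies to someone who withdraws consent and refuses the early-termination visit and, if it does not, say so in 9.2.

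The cost is up to about 40 short calls by existing staff (at most about 6 if limited to early leavers at the assumed dropout), plus small text changes. No dose, visit or clinical rule changes.

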9.3 Characteristics of an Adverse Event

9.3.1 Relationship to Study Intervention

To assess relationship of an event to study intervention, the following guidelines are used:

- 1. Related (Possible, Probable, Definite)
 - a. The event is known to occur with the study intervention.
 - b. There is a temporal relationship between the intervention and event onset.
 - c. The event abates when the intervention is discontinued.
 - d. The event reappears upon a re-challenge with the intervention.
- 2. Not Related (Unlikely, Not Related)
 - a. There is no temporal relationship between the intervention and event onset.
 - b. An alternate etiology has been established.

9.3.2 Expectedness of SAEs

AMGEN and the Study PI will be responsible for determining whether an AE/SAE is expected or unexpected.

The most common adverse reactions (incidence ≥ 3% and more often than placebo) in the migraine studies were injection site reactions and constipation. Common side effects that may affect between 1 and 10 people in every 100:

- Injection site reactions: which may include tenderness, pain, redness, itching, bruising, firmness, or hypersensitivity
- Constipation
- Muscle spasms/cramps

Itching (pruritus)

Since erenumab was approved in May 2018, the following events have been reported in patient's exposed to erenumab in the post-marketing setting:

- 1)Severe allergic reactions such as rash, swelling and difficulty breathing, or swallowing.
- 2) Mouth/lip sores (e.g., stomatitis, mouth ulcerations, and oral mucosal blistering)
- 3) Skin and subcutaneous tissue disorders
- o Alopecia (loss of hair)
- o Rash (e.g., papular rash [small raised red rash], exfoliative rash [redness and/or peeling of skin], erythematous rash [red rash], urticaria [hives], and blisters)
- 4)Constipation and the use of medications that decrease gastric motility are in our exclusion criteria, however if a new onset of constipation occurs, the participant will be withdrawn of the study and will be referred to an appropriate practitioner for continued care (see section 9.2).
- 5) Hypertension or worsening of high blood pressure can happen after receiving Erenumab. Hypertension is in our exclusion criteria, however if a new onset of hypertension occurs, the participant will be withdrawn of the study and will be the participant will be referred to an appropriate practitioner for continued care (see section 9.2)

An adverse event (AE) will be considered unexpected if the nature, severity, or frequency of the event is not consistent with the risk information previously described for the intervention, protocol, investigator's brochure and/or informed consent document.

9.3.3 Severity of Event

Severity grades will be based on the Common Terminology Criteria for Adverse Events (CTCAE)

grade 1 = mild; grade 2 = moderate; grade 3 = severe or medically significant; grade 4 = life-threatening consequences; and grade 5 = death.

9.4 Reporting Procedures

9.4.1 Unanticipated Problem Reporting to IRB and AMGEN

[figure not shown]
Incidents or events that meet the OHRP criteria for unanticipated problems require the creation and completion of an unanticipated problem report form within the Electronic Data Capture (EDC) system. Following OHRP recommendations the investigators will include the following information when reporting an adverse event, or any other incident, experience, or outcome as an unanticipated problem to the IRB and AMGEN Safety:

- Appropriate identifying information for the research protocol, such as the title, investigator's name, and the IRB project number.
- A detailed description of the adverse event, incident, experience, or outcome.
- An explanation of the basis for determining that the adverse event, incident, experience, or outcome represents an unanticipated problem.
- A description of any changes to the protocol or other corrective actions that have been taken or are proposed in response to the unanticipated problem.

• All unanticipated problems will be reported to appropriate institutional officials (as required by an institution's written reporting procedures), the supporting agency head (or designee), and OHRP within one month of the IRB's receipt of the report of the problem from the investigator.

[figure not shown]
All unanticipated problems will be reported to AMGEN Safety via email by the investigator. These reports will be reviewed by the IRB.

[figure not shown]

9.4.2 Serious Adverse Event Reporting to AMGEN Safety and UMB IRB

Any AE meeting the specified Serious Adverse Event criteria will be submitted on an SAE form to the IRB and AMGEN Safety.

The PI will complete a Serious Adverse Event Form and submit via fax or email within the following timelines:

- All deaths and immediately life-threatening events, whether related or unrelated, will be recorded on the Serious Adverse Event Form and submitted to Product Safety within 24 hours of site awareness.
- Serious adverse events other than death and immediately life-threatening events, regardless of relationship, will be reported by fax within 72 hours of site awareness.

All SAEs will be followed until resolution or stabilization.

9.4.3 Reporting of SAEs and AEs to FDA

FDA reporting is not applicable.

9.4.4 Events of Special Interest (if applicable)

Any clinically significant finding of worsening of a medical condition other than Trigeminal Neuropathic Pain (TNP) established at baseline/Visit 0 or the development of any new clinically significant medical condition throughout the study will be considered an AE and will be reported as described previously.

9.4.5 Reporting of Pregnancy

If a participant becomes pregnant at any time during the study, it will be recorded on a case report form within the EDC system. Pregnancy/lactation exposure and any associated reports/outcomes (i.e. unexpected pregnancy, pregnancy of partner, spontaneous abortion, congenital anomaly etc.) will be reported within 1 business day of sponsor/PI awareness, for reports meeting serious criteria and not to exceed 15 calendar days of sponsor awareness, for non-serious reports to IRB and AMGEN Safety (As mentioned on 9.4.2 Table 2).

Participants who become pregnant while participating in the study will be withdrawn from the study and referred for appropriate care. If a participant becomes pregnant while receiving the study drug, she will be followed for safety until a pregnancy outcome is reached. If the pregnancy results in an outcome other than a normal birth or elective abortion of a healthy fetus, it will be reported as an SAE.

9.5 Halting Rules

This is addressed in Section 5.6. Based on the findings of a (scheduled or ad-hoc) safety review, the study may be temporarily suspended to enrollment (or to an intervention), or it may be prematurely terminated.

Depending on the findings of a safety review, the medical monitor, UMB (sponsor) IRB, or the DSMB will determine whether the study: should continue per protocol; proceed with caution; be further investigated; be modified; or be terminated.

Some types of events that might trigger a safety review are: number of SAEs overall; prevalence of a specific SAE; number/type of severe AEs; or increased frequency of AEs.

10 STUDY OVERSIGHT

In addition to the PI's responsibility for oversight, study oversight will be under the direction of a Data and Safety Monitoring Board (DSMB) composed of members with expertise in pain management and orofacial pain management at the sponsor site . The PI, and DSMB will meet on a predetermined schedule to assess safety and efficacy data, study progress, and data integrity for the study.

11 CLINICAL SITE MONITORING

Clinical site monitoring is conducted to ensure that the rights of human subjects are protected, that the study is implemented in accordance with the protocol and/or other operating procedures, and that the quality and integrity of study data and data collection methods are maintained. Monitoring for this study will be performed by the IRB UMB The monitor will evaluate study processes and documentation based on IRB UMB standards and the International Conference on Harmonisation (ICH), E6: Good Clinical Practice guidelines (GCP).

12 STATISTICAL CONSIDERATIONS

12.1 Study Hypotheses

The primary efficacy hypothesis is a higher proportion of participants in Erenumab group will achieve at least 30% reduction in monthly average pain score from baseline (monthly data prior to Visit 1) to end of treatment (monthly data prior to Visit 4) than those in placebo group.

The secondary efficacy hypothesis:

To investigate the efficacy of Erenumab compared to placebo on the reduction in monthly average daily pain score from baseline to the end of 12-week treatment period.

To investigate the efficacy of Erenumab compared to placebo on the proportion of subjects who achieved a least 30% reduction in the monthly average daily pain score from baseline to Visit 5 (follow-up/final visit).

To determine the efficacy of Erenumab using functional measures related to TNP impact in daily activities, disability and emotional functioning measured by questionnaires (GCPAs, HADS, PGIC and PENN Facial Pain Scale).

The exploratory hypothesis:

12.2 Sample Size Considerations

The sample size was calculated based on the primary objective to compare the percentage of participants who had at least 30% reduction in pain from baseline to end of the treatment between experimental groups. Gomez-Arguelles et al. reported a reduction in pain frequency in days from 12.26(SD, 3.86) at baseline to 5.16(SD, 2.16) after 12 weeks anticonvulsants therapy for a group of trigeminal neuropathic pain patients [47] The changes was estimated as a very large effect size Cohen's d=2.1. The effect size in the animal studies has also been shown to be extremely large, approximately of 7 SD [48]. We assume the proposed trial will have a large effect size with Cohen's d=.8 or OR=4.2. Based on this assumption and two-sided type I error of α =.05, a sample of n=36 will provide sufficient power (Power >80%) to detect a large effect size between two groups [49]. This effect size could be interpreted as that about 58% of the participants in intervention group will reach at least 30% reduction in pain scores at the end of treatment

while 25% occur in the placebo group. Considering a 15% overall dropout rate, we will recruit N=40 participants (20 in each experimental group).

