12.3 Final Analysis

Descriptive statistics including measures of central tendency, dispersion and appropriate visualization approaches (e.g., box plots and spaghetti plots) will be performed on each outcome variable (pain scores, and outcomes in secondary and exploratory objectives) by time points and groups. This will be done to ascertain distributional characteristics and ensure that the assumptions (e.g., normality) associated with the planned statistical procedures are met. When necessary, transformations will be performed. All analyses will be done in SAS and will follow an intent-to-treat philosophy.

The main goal of the statistical analyses is to compare the changes in study primary and secondary endpoints between groups to evaluate efficacy of Erenumab. For the primary objective, the generalized Linear Mixed Models (GLMM) with binomial distribution will be used to assess the efficacy of Erenumab on the primary endpoint (i.e., at least 30% reduction in pain score; yes/no). The fixed effects included in the models will be treatment group (intervention versus placebo), time (dummy coded from baseline to visits 2-4), and the interaction terms of group by time. The random effects include the participants to account for correlations between repeated measures. The primary hypothesis will be tested by evaluating the interaction term of group and time from baseline to visit 4. In the meantime, the Erenumab efficacy from baseline to visits 2 and 3 will be evaluated through the interaction terms at the corresponding time points. The secondary objective of the difference in change (>30% reduction) from baseline to visit 5 will also be evaluated using the similar GLMM model with the corresponding time (baseline, V2-V5), group and interaction terms between time and group. The interaction of time (baseline to V5) and group will be evaluated to test the hypothesis. The difference from V4 to V5 will also be evaluated by contrast estimation from the model. We will use a significance level of twosided α < 0.05 as primary hypothesis test.

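### Section 12.2 claims more than 80% power at n=36 for 58% vs 25% responders; standard two-sided two-proportion tests give about 43–57%

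*Combined protocol and SAP*

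**What the plan says.** Section 12.2 ties the calculation to the primary, binary endpoint: "The sample size was calculated based on the primary objective to compare the percentage of participants who had at least 30% reduction in pain". The assumed effect is given on two scales, "We assume the proposed trial will have a large effect size with Cohen's d=.8 or OR=4.2", with two-sided alpha 0.05. The section then states that "a sample of n=36 will provide sufficient power (Power >80%) to detect a large effect size between two groups". It translates the effect as "about 58% of the participants in intervention group will reach at least 30% reduction in pain scores at the end of treatment", against 25% on placebo. Last comes the allowance for loss: "Considering a 15% overall dropout rate, we will recruit N=40 participants (20 in each experimental group". The 36 is therefore a total of 18 per arm. No test, number of repeated measures or within-participant correlation is given for the power figure.

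Section 12.3 plans a binomial generalized linear mixed model with "time (dummy coded from baseline to visits 2-4), and the interaction terms of group by time". On the test itself it says: "The primary hypothesis will be tested by evaluating the interaction term of group and time from baseline to visit 4".

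**The concern.** A difference of 33 percentage points between two arms of 18 is a small-sample binary comparison, and power above 80% looks too high for it. This is the only power figure in the plan and it concerns the primary endpoint. The IRB, the funder and readers will use it to judge what the trial can show. If it is overstated, a null result may be read as evidence against erenumab when the trial had roughly an even chance of missing the assumed effect. Section 5.6 also lists futility as a possible ground for termination, so the figure could influence oversight too.

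**Working it through.** **Inputs (all Section 12.2).** p1 = 0.58, p2 = 0.25, two-sided alpha 0.05 (z = 1.96), OR = 4.2, d = 0.8, 36 in total, 15% dropout, N = 40. Allocation is 1:1 (Section 5.4.1).

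**Are the effect sizes consistent?** Yes.
- OR from 58% and 25%: (0.58/0.42)/(0.25/0.75) = 4.14.
- OR 4.2 with 25% placebo: odds 4.2 × 0.3333 = 1.4, so 1.4/2.4 = 58.3%.
- d = 0.8 to OR: exp(0.8π/√3) = 4.27.

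**Trying to reproduce the stated power at n = 18 per arm.**

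Pooled z: power = Φ{[(p1 − p2) − 1.96·s0]/s1}, where s0 = √(2·p̄(1 − p̄)/n), s1 = √([p1(1 − p1) + p2(1 − p2)]/n) and p̄ = 0.415.
- s0 = √(2 × 0.415 × 0.585/18) = 0.1642
- s1 = √((0.2436 + 0.1875)/18) = 0.1548
- Φ[(0.33 − 0.3219)/0.1548] = Φ(0.052) = **52.1%**

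Unpooled z: Φ(0.33/0.1548 − 1.96) = Φ(0.172) = **56.8%**.

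Wald test of the log odds ratio: ln 4.14 = 1.421, SE = √(1/(18 × 0.2436) + 1/(18 × 0.1875)) = 0.724; Φ(1.421/0.724 − 1.96) = **50.1%**.

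Fisher and Pearson chi-square power come from summing binomial probabilities over all outcomes that reject.

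| Per arm | Fisher | Wald log OR | Pooled z | Unpooled z | Exact chi-square |
|---|---|---|---|---|---|
| 17 | 38.1% | 47.9% | 49.7% | 54.5% | 52.5% |
| 18 | 42.9% | 50.1% | 52.1% | 56.8% | 57.1% |
| 20 | 44.5% | 54.3% | 56.7% | 61.3% | 56.3% |

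The chi-square value at 18 per arm is generous: the test's type I error there is 6.0% at a common rate of 40%, and up to 6.5%.

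**Size needed for 80%.** Pooled z: 34 per arm (80.3%). Unpooled z: 32 per arm. Fisher: 40 per arm (81.5%; 39 per arm gives 79.7%).

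**Is the 25% placebo rate the cause?** No. With the OR held at 4.2 and the placebo rate varied from 5% to 70%, the best power on any of pooled z, unpooled z, chi-square or Fisher is 60.5% at 18 per arm and 64.0% at 20.

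**Other readings.**
- Two-sample t-test at d = 0.8, 18 per arm (noncentrality 0.8 × √9 = 2.4, 34 df): 64.5%; 80% needs 26 per arm.
- One-sided 0.05, which the plan does not use: 65.1% (pooled z) or 76.0% (t-test).
- 36 *per arm*: 82.5% (pooled z). This matches the claim but contradicts N = 40.
- Between-group test in a repeated-measures ANOVA of a continuous outcome, f = 0.4, 36 in total, noncentrality f²·N·m/[1 + (m − 1)r]. With m = 3 and r = 0.5 this is 0.16 × 36 × 3/2 = 8.64, power 81.5%. With m = 3 and r = 0.7 it is 74.1%; with m = 2 and r = 0.5, 76.8%. These settings are assumed; the documents give none.

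**Dropout.** 40 × 0.85 = 34, not 36. Forty covers 1 − 36/40 = 10% loss. Keeping 36 after 15% loss needs 36/0.85 = 42.4, so 43 (44 for equal arms).

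**What N = 40 can show.** Against 25% placebo, the erenumab rate detectable with 80% power (pooled z) is 67.9% at 20 per arm and 71.4% at 17. The expected 95% CI half-width for the risk difference, 1.96 × √(0.4311/n), is 28.8 points at 20 per arm and 31.2 at 17.

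**The case against.** The strongest objection is that the primary test is not a two-proportion test. It is a group-by-time interaction in a binomial mixed model, and its power could differ. That stands as a limit on what is shown: the 43–57% is a benchmark, not the power of the planned test. It does not support the stated figure. The test targets Visit 4 specifically, no within-participant correlation or Visit 2–3 responder rates are given, and the model includes baseline as a time level, where nobody can yet be a responder.

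A second objection is that some continuous-outcome calculations do exceed 80% at 36 in total. Besides the repeated-measures case above, a baseline-adjusted comparison at d = 0.8 gives 76.7%, 82.9% and 90.3% for assumed baseline correlations of 0.5, 0.6 and 0.7. A within-between interaction with f = 0.4, three measures and r = 0.5 gives over 99%. One of these may be where the figure came from. None is the power for the binary Visit 4 endpoint that Section 12.2 says it sized.

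Third, the protocol calls this a pilot (Sections 2.1 and 4). A pilot may be small, but Section 12.2 makes a formal power claim and Section 12.3 sets a significance test, so the number still has to be right.

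Fourth, 17 per arm is pessimistic: Section 7.5 repeats Visit 4 procedures at early termination, and Section 12.3 relies on maximum likelihood for missing data. That is fair, so it is used here only as a lower-end assumption.

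**Conclusion.** The concern holds. The stated power cannot be reproduced from the plan's own inputs for a binary comparison at 36 in total. Benchmark power is 43–57% at 18 per arm and about 44–61% if all 40 are analysed, so the assumed effect would be missed about 43–57% and 39–56% of the time respectively, rather than under 20%. At 17 per arm the misses rise to about 46–62%. Reaching 80% would take 64 to 80 analysed participants (32 to 40 per arm), depending on the test. These results assume 58% vs 25%, two-sided 0.05, equal arms and a single comparison at Visit 4. The dropout arithmetic is a separate and smaller error.

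**What to change.** Keep N = 40, delete the claim of power above 80%, and replace the end of Section 12.2 with wording such as:

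> As a benchmark, not the power of the planned GLMM test, a simple two-sided two-proportion comparison of 58% vs 25% at alpha .05 has about 57% power with 20 per arm (pooled z; 44% Fisher, 61% unpooled z). If all 15% dropout leaves participants without Visit 4 data (17 per arm, a lower-end assumption), power is about 50% (38% Fisher, 54% unpooled z). Against a 25% placebo rate, the erenumab rate detectable with 80% power is about 68% at 20 per arm and 71% at 17 per arm (pooled z). The expected 95% CI half-width for the risk difference is about 29 to 31 percentage points. A non-significant result is not evidence of no effect.

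This also removes the inconsistent step from 36 to 40. If the original figure came from a continuous-outcome calculation, repeated-measures or baseline-adjusted, state its outcome, number of measures and correlation, and say that it is not the power for the binary Visit 4 endpoint.

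The cost is wording only: no extra participants, visits or data. As an amendment it needs review and approval by AMGEN and the IRB (Section 15.2), and the stated power will look less favourable.
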